Participant contact: The research team will utilize both email and Avocado (a messaging platform that facilitates text message communication between research staff and study participants without staff member using their personal phone numbers for the study; already vetted by the OIT) when communicating with participants in the study. Access to Avocado inbox used for this study will be limited to necessary study staff. Participants will be asked to indicate their preferred method of contact on the contact form (after consent) and will be contacted only via their selected method.

Baseline (T1), post-intervention (T2), and 3-month follow-up assessments (T3): At each timepoint, participants will complete a Qualtrics survey, which will be accessed through a unique link created based on each participant's deidentified participant identification number (PID).

The Baseline assessment (T1) will include a set of sociodemographic questions as well as a total of 27 scales, measuring depression, anxiety, PTSD, functional impairment due to depression, functional impairment due to anxiety, interoceptive awareness, de-centering, rumination/perseverative thinking, theories of psychological distress, theories of emotion, internalized stigma, emotion regulation, loneliness, mindfulness, self-compassion, perceived stress, political stress, sleep, phone use, early life adversity, childhood trauma, experiences of stress and adversity, everyday experiences of discrimination, rejection sensitivity, Major Depressive Episode, Generalized Anxiety Disorder, and overall well-being (see "Compiled Measures_GEM.docx").

Additionally during the Zoom call for baseline assessment (T1), the RA will "onboard" the participant and (a) review how to use a FitBit, (b) install the study application, and (c) problem solve any logistic issues. The baseline assessment and onboarding will take a total of 90-120 minutes.

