Data analysis: Feasibility, acceptability, and preliminary effects will be assessed using data from the T1, T2, and T3 surveys as well as EMA responses. Qualitative data analysis will also be performed for the exit-interviews and voice recordings to further qualify our findings after transcription and deidentification. Exit interviews will be transcribed using Dedoose (already vetted through OIT), while EMA voice recordings will be transcribed automatically through Expiwell's AWS service. Additionally, recruitment and retention rates, completion of weekly modules, adherence to daily EMA and EMI prompts, weekly session attendance, and other engagement metrics from the application (e.g., frequency of EMI-triggered vs. self-initiated practice use, time spent in modules) will be used to inform study and intervention feasibility.

- 6.3 We will take all reasonable precautions to prevent adverse events to participants. As a meditation-based intervention, a number of actions have been taken to minimize meditation-related risks at different stages of the study. During the pre-enrollment stage, individuals with severe mental

illness that could preclude regular class attendance or impact group participation (i.e., symptomatic, untreated bipolar disorder or a history of psychosis and/or schizophrenia) are excluded from the study. During treatment, meditations are created to be relatively short and interspersed with dyads and reflections to minimize probability of risk. Developing strategies for working with physical and emotional discomfort is also an explicit goal of the program.

No drugs will be administered as part of this study. The only devices used are a) the participant's personal cell phone with the intervention content loaded through the Expiwell app and b) a wearable device Fitbit, which is commercially available and FDA-cleared for general wellness monitoring; it will be used solely to collect sleep and physiological data.

For all assessments and guides used for data collection, please refer to the document named "Compiled measures_GEM.docx".

6.4 A list of all data that and how they will be collected during the study is listed below:

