10.0 Inclusion and Exclusion Criteria

- 10.1 Screening survey: Individuals interested in the study will access a Qualtrics survey via recruitment links. The survey will be developed based on the study's inclusion and exclusion criteria (except for imminent risk of suicide and current Major Depressive Episode, which will be assessed during the Zoom screening interview). Scores on screening measures within the survey will be calculated in real time using Qualtrics' scoring feature—if a potential participant's score meets the study's inclusion threshold (see section 10.2), the survey flow will set an embedded variable ("eligible") to true; otherwise, it will be set to false. Statement addressing the legal concerns of underage consumption of alcohol and illegal substance use has been added to the screener.

Individuals who meet the eligibility criteria will be redirected to a separate Qualtrics form where they can review the Informed Consent Form (ICF) and complete a contact form, which will collect their full name and email address. These individuals will also be asked if they would like to be notified for future research. Please refer to the document named "Compiled measures_GEM.docx" for the screening survey, contact form, and future contact form. A trained research staff will then follow up with the eligible participants to schedule a Zoom-based screening interview.

Zoom screening interview: The interview will take 15-30 minutes to complete and will serve the following purposes: (a) confirm participant eligibility and identity by participant showing any form of ID including photo, name, and age; (b) review informed consent form; (c) review study procedures and answer any questions the participant may have; (d), screen for current Major Depressive Episode and imminent risk of suicide; and (e) inform the participant (if eligible and interested to enroll) of the next steps, which includes the next Zoom call meeting for baseline assessment and onboarding (refer to section 6.2). At the beginning of the screening call, RA will remind participants that if they disclose information indicating imminent risk of serious harm to themselves or others, this information must be reported to relevant law enforcement or other authorities. The RA conducting this interview will use a Qualtrics survey with the questions/measures that need to be administered (e.g., the MINI-Major

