 - Did you ever miss school due to fear of being bullied?
 - Were you ever injured or threatened with a weapon or otherwise assaulted by a peer at school?
 - Were you ever physically attacked, hit, hurt, or injured by a parent, primary caregiver, or guardian?
 - Were you ever touched sexually against your wishes or forced to touch someone else sexually?
 - Were you ever forced to engage in sexual intercourse?
 - Were you ever forced to have sex or were you ever sexually abused (e.g., being touched or fondled by an adult?)

- (4) Experience more than minimal symptoms of anxiety (GAD-7 score of 5 or higher) and/or mild to moderately severe depression symptoms (PHQ-9 score between 5–19)
- (5) Not currently in mental health treatment
- (6) Being willing to answer 3–4 short surveys daily, each 2–5 mins
- (7) Being willing to engage in recommended daily mindfulness practices for 4–6 weeks
- (8) Have not been extensively exposed to mindfulness, defined as meditation retreat experience, consistent mindfulness practice (> once/week) within the past 6 months, or prior participation in a mindfulness course/program

Exclusion criteria:

- (1) At imminent risk of suicide
- (2) Have a history of psychotic disorder (e.g., schizophrenia) or psychotic episode
- (3) Have a current diagnosis of Major Depressive Disorder
- (4) Meet the criteria for Major Depressive Episode based on the MINI-Major Depressive Episode module at screening
- (5) Score 20 or higher on Alcohol Use Disorders Identification Test (AUDIT) at screening
- (6) Score 25 or higher on Drug Use Disorders Identification Test (DUDIT) at screening
- (7) Have ever been diagnosed with bipolar disorder

10.3 We will not include any of the listed special populations in this research.

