15.0 Risks to Subjects

- 15.1 Meditation-related risks: The National Center for Complementary and Integrative Health (NCCIH) states that meditation is generally safe for healthy people, but that adverse effects have also been reported. More common, less serious side effects that have been reported by individuals within the context of MBIs or of individuals who are meditating less than an

hour per day include: increased depression, anxiety or panic, re-experiencing of traumatic memories, dissociation, executive dysfunction, headaches/body pain and insomnia. A few case reports of more serious side effects including mania, psychosis, and suicidality have been reported, mostly in the contexts of intensive retreats (>5 hrs/day) or in conjunction with pre-existing psychopathology. The frequency of serious adverse effects in the context of MBIs is estimated to be less than 1%, although adequate estimates are not available.

Psychological distress: Research subjects participating in this study may experience possible psychological distress caused by questions asked during the in-person and online questionnaires that bring up painful memories or feelings. However, the resulting potential for injury to research subjects is judged to be minimal. With regard to psychological distress from taking part in the intervention, given that screening questions will exclude participants with substantial mental illness, and given the NCCIH statement above that “meditation is considered to be safe for healthy people,” we expect that the risk will be low.

Loss of confidentiality: Confidentiality will be maintained by using deidentified data sets. All electronic data files containing identifying information will be encrypted with cloud-based software. Although these measures have been taken to protect participants’ personal information and the likelihood of loss of confidentiality is minimal, complete confidentiality cannot be guaranteed when transmitting information over the internet. All information obtained from participants will be accessible only to research staff.

Risks Related to Wearable Devices: Wearing the Fitbit device may cause minor physical discomfort (e.g., skin irritation) or inconvenience in daily routines.

Oversight of internal monitoring of the participants’ safety will be conducted by the PI, [name], who is a licensed psychologist.

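### The bipolar exclusion in Protocol 10.2(7) is stricter than 6.3 for diagnosed people but has no episode rule, so undiagnosed manic or hypomanic symptoms can pass

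*Protocol*

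**What the plan says.** Protocol 6.3, on actions taken before enrollment to limit meditation-related risk, says that people with severe mental illness that could interfere with attendance or group participation are kept out, and specifies: "i.e., symptomatic, untreated bipolar disorder or a history of psychosis and/or schizophrenia) are excluded from the study".

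Protocol 10.2 sets the operative rules:

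- Exclusion (7), bipolar disorder: "Have ever been diagnosed with bipolar disorder".
- Exclusion (2), psychosis: "Have a history of psychotic disorder (e.g., schizophrenia) or psychotic episode".
- Exclusions (3) and (4), depression: a current diagnosis of Major Depressive Disorder, or meeting Major Depressive Episode (MDE) criteria on the MINI module at screening.
- Inclusion (5): "Not currently in mental health treatment".

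Protocol 10.1 ties the online screener to these rules: "The survey will be developed based on the study's inclusion and exclusion criteria", with MDE and suicide risk left to the Zoom interview. The clinical purpose given for that interview is to "screen for current Major Depressive Episode and imminent risk of suicide".

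Protocol 15.1 says of meditation: "A few case reports of more serious side effects including mania, psychosis, and suicidality have been reported". It places these mostly in intensive retreats or in people with existing psychopathology. It rests its low-risk expectation for the intervention partly on screening questions that keep out substantial mental illness. The SAP does not address eligibility.

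**The concern.** Sections 6.3 and 10.2(7) draw the bipolar boundary differently. The first turns on present symptoms and lack of treatment, the second on whether a diagnosis was ever made. Because 10.1 builds the screener on 10.2, the second decides who enters.

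A rule that depends on diagnosis is weakest among people outside care, and inclusion (5) restricts the study to people not in current treatment. The neighbouring criteria do not share this dependence: psychosis can be excluded on an episode, and depression on a structured interview that needs no prior diagnosis. At stake is whether the entry rule delivers the protection that 6.3 describes and on which 15.1 partly relies. The estimates, feasibility benchmarks and sample size are not in question.

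**Working it through.** No arithmetic decides this point. The check sets the texts side by side.

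**Step 1: what 6.3 requires in this sample.** Inclusion (5) means every entrant is currently untreated. The untreated condition in 6.3 is therefore met by everyone, and only the symptomatic condition separates people. Section 6.3 does not mention diagnosis.

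**Step 2: compare the rules.** Take people with a non-psychotic manic or hypomanic episode, now or in the past, who are not in treatment:

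| Case | 6.3, read literally | 10.2(7) |
|---|---|---|
| Diagnosed, symptomatic | excluded | excluded |
| Diagnosed, not symptomatic | not excluded | excluded |
| Never diagnosed, symptomatic | excluded | not excluded |
| Never diagnosed, not symptomatic | not excluded | not excluded |

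In the second row 10.2(7) is the more protective text. In the fourth row the texts agree. Only the third row is a shortfall of 10.2(7) against 6.3. The rows are logical cases and say nothing about how many people fall in each.

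**Step 3: remove those caught by other criteria.** Exclusion (2) removes anyone with a psychotic episode, so psychotic mania is covered. Exclusion (4) removes anyone in a current MDE, diagnosed or not. What remains of the third row is a never-diagnosed person with manic or hypomanic symptoms, no psychotic history and no current MDE. The AUDIT and DUDIT limits remove some of these for other reasons.

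**Step 4: look for a described procedure that closes the gap.** The Zoom interview is described as covering MDE and suicide risk. At T1 the protocol gives sociodemographic questions "as well as a total of 27 scales", and none of the listed constructs is mania. The MINI modules named for T1 to T3 are MDE and generalized anxiety only. The T1 content is weak evidence because it comes after eligibility is settled. The screener and interview checklist are separate files that were not supplied.

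**Step 5: what the documents allow on size.** Section 15.1 puts all serious effects of mindfulness programmes together below 1% and adds that adequate estimates are lacking. With 44 participants, 44 × 0.01 = 0.44, so fewer than 0.44 serious events of any kind would be expected. Mania is an unstated part of that. This bounds the general background and does not measure the gap. No rate of undiagnosed manic or hypomanic episodes is given, so no probability of enrolling such a person can be derived.

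**The case against.** The strongest reply is that 10.2(7) is already the tougher rule. It is lifetime, and it applies whether or not symptoms are present. A reader might infer from the mismatch that the bipolar exclusion in 6.3 never reaches the operative criteria. The documents do not support that: for everyone with a diagnosis it is there in broader form.

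A second reply is that the phrase in 6.3 is a gloss on illness severe enough to disrupt participation, and may mean a known disorder left untreated. On that reading 10.2(7) contains it fully and the texts do not conflict. This is a fair reading, so the claim is only that 6.3 can be read to cover undiagnosed people. The absence of an episode rule in 10.2(7) does not depend on it.

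Third, a mania question may exist in the files not supplied. That would narrow the practical gap. But nothing in 10.2 would make a positive answer from an undiagnosed, non-psychotic applicant disqualifying. A reader might also infer that nobody is asked about mania; the documents cannot show this.

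Fourth, a lifetime episode rule goes further than 6.3, because it also removes undiagnosed people in remission. That is correct. The extension follows the pattern of exclusion (2), which uses history, and is offered as an improvement, not as the repair of a contradiction.

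Finally, a reader might count the silence of 14.1 on mania as a second gap. That list of withdrawal grounds is worded as open-ended, so it shows no defect.

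**Conclusion.** The point holds in a narrow form, as a minor improvement. The two sections define the bipolar exclusion differently. Section 10.2(7) is stricter where there is a diagnosis, and is silent on undiagnosed, non-psychotic manic or hypomanic symptoms without a current MDE.

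The frequency of such applicants is unknown from the documents. The absolute risk is small: the meditations are short, adverse events are monitored (4.2), EMA responses are reviewed daily, there are weekly live sessions, and the investigator is on call for safety concerns. Endpoints and analysis are unaffected.

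The conclusion assumes that 10.2 is the rule actually applied, as 10.1 states. Calling it a shortfall against 6.3 also assumes that 6.3 is not confined to known disorders.

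**What to change.** 1. Extend 10.2(7) so that it reads: "Have ever been diagnosed with bipolar disorder", or report a current or past manic or hypomanic episode.
2. Put one question in the existing online screener, if none is there already, and confirm it at the existing Zoom interview. It should describe the symptoms in plain terms, because someone never diagnosed cannot be expected to recognise the label of a manic episode.
3. Reword 6.3 to match the revised 10.2(7). This also settles the diagnosed but stable person, whom 6.3 would not exclude and 10.2(7) does.

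The cost is one question, a short confirmation in an interview already planned at 15 to 30 minutes, and edits to two sections. The drawback is that some applicants, including false positives, will be screened out on self-report; the documents do not allow that number to be estimated. Section 14.1, the sample size, the endpoints and the analysis need no change.

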11.0 Vulnerable Populations

11.1 N/A

12.0 Local Number of Subjects

12.1 We anticipate enrolling 44 *participants in the single-arm trial*.

12.2 A larger number of young adults will be screened for eligibility, and 44 participants will be recruited to enroll in the single-arm trial. From these 44 participants, we aim to have at least 35 participants (i.e., approximately 80%) who complete all intervention procedures and follow-up assessments. Screening more participants ensures that we can meet the target enrollment despite ineligible candidates, and enrolling more ensures that we collect enough data points even with potential withdrawals.

13.0 Recruitment Methods

13.1 We will implement a nationwide, remote recruitment strategy using a multi-pronged approach. Potential participants will be recruited over a 2–3 month period from various recruitment sources: (1) providing IRB approved recruitment materials (see section 13.4) to CAB members for them to distribute to their social networks and post on their social media accounts; (2) posting recruitment materials on online social media, such as Facebook-based community groups, Reddit threads, X, etc.; (3) targeted recruitment through OpenClinica (also formerly known as BuildClinical and vetted and approved by Brown OIT; OpenClinica is a specialized service that uses targeted digital outreach and pre-screening to connect

researchers with qualified participants by running data-driven digital advertising campaign across their digital network;); (4) sending emails to university/college campus groups, community-based organizations, and partner health groups (e.g., Project Weber/RENEW)—the email will include the recruitment material and a script, which the organizations can use to share information directly with potentially eligible participants (e.g., via email) or post the materials on their community channels (e.g., newsletters, listservs, websites); and (5) sharing study information on Today@Brown, a daily email delivered to all students, faculty and staff at Brown (also refer to [[contact]](#) for language). Specifically, OpenClinica's involvement in recruiting is in digital outreach (e.g., using targeted digital ads through their pre-existing channels). It connects researchers with potential participants by engaging and generating leads from individuals interested in the study, and these individuals will be provided with link to the study team's Qualtrics survey screener. Therefore, OpenClinica itself will not have any access to identifiable information or the screening survey, independently perform consent, make screening decisions, or enroll participants into the study; instead, those will remain as functions of the research team, per the screening protocol described in this document. Please refer to the document titled "Recruitment Email Drafts_GEM.docx" for the email draft as well as the written script, which will be used to explain the study purpose and procedures.

- 13.2 The source of participants will be local and online communities where individuals with lived experiences of early life adversities and mental health challenges may be present. These communities include, but are not limited to social networks, LGBTQ+ groups, foster care and youth residential programs, and networks that provide support for survivors of abuse and violence.
- 13.3 Potential participants will be identified by having them self-report their age, experiences of early life adversities, and depression or anxiety symptoms through the screening Qualtrics survey. The research team will contact individuals for further screening (i.e., schedule Zoom screening interview) if they are deemed potentially eligible from the screening survey (see Sections 10.1 and 10.2).
- 13.4 Other than the email draft and written script described in Section 13.1, recruitment materials will include flyers and graphics for social media posts. Each material will provide a brief study description, eligibility criteria, and contact information. Please refer to the files titled "Recruitment_GEM.docx" for flyers and social media graphics. Furthermore, recruitment materials created by OpenClinica will be submitted to the IRB for review when they are created, after a contract is finalized.
- 13.5 Participants will only be compensated for the study components that they choose to complete. If a participant withdraws from the study early, they will not be compensated for the study components that are incomplete. Compensation will be provided through Amazon gift cards. Total possible compensation for participants is \$168:

Study Procedure	Compensation	Compensation period
-----------------	--------------	---------------------

Baseline assessment (T1)	\$25	Paid after survey completion
Ecological momentary assessment (during the first 4 weeks of intervention period; i.e., recommended modules)	Maximum of \$56: \$2/day for completing at least 2 of 3 daily EMA prompts over a maximum of 28 days (i.e., 4-weeks)	Paid in a single installment at the end of Week 4
Weekly assessments (during the first 4 weeks of intervention period; i.e., recommended modules)	Maximum of \$12: \$3 for completing each assessment, once a week over 4 weeks	
Post-intervention assessment (T2)	\$25	Paid after (1) survey/interview completion AND (2) Fitbit device is returned to the study team
Exit interview (T2)	\$25	
Follow-up assessment (T3)	\$25	Paid after survey completion

